3. OVERALL STUDY DESIGN

3.1. Study Design

This is a Phase 2 multi-center, open-label, parallel-group study that will assess the efficacy, safety and tolerability of pomalidomide in children and young adults aged 1 to < 21 years with recurrent or progressive primary brain tumors after at least one prior standard therapy.

The study will consist of 4 parallel strata, one for each of the following primary brain tumor types: high-grade glioma, medulloblastoma, ependymoma and DIPG. A Simon's Optimal two-stage study design will be applied to each stratum and enrollment will occur as follows:

- Stage 1: Nine subjects will be enrolled.
- Stage 2: If during Stage 1, ≥ 2 subjects achieves either an OR (either CR or PR) within the first 6 cycles of treatment (within first 3 cycles for DIPG), or a long-term SD, an additional 11 subjects shall be enrolled; otherwise no additional subjects will be enrolled into that stratum.
- If a total of 5 or more subjects across all 20 subjects in a given stratum (Stage 1 and 2) evaluable for the primary endpoint are observed as having either an OR (either CR or PR) within the first 6 cycles of treatment (within first 3 cycles for DIPG) or a long-term SD, pomalidomide will be considered effective in that disease indication.

Subjects who withdraw from either stage for reasons other than PD prior to completing Cycle 1 of study treatment will be replaced. Subjects completing at least one cycle of study therapy but not having at least one post-baseline disease assessment will be considered a non-responder.

The study will have the following sequential periods for all subjects (Figure 2): Screening Period (Section 6.1), Treatment Period (Section 6.2) and Follow-up Period (Section 6.3). Upon enrollment, subjects will receive oral pomalidomide for the first 21 days, followed by a 7-day rest period, of each 28-day treatment cycle for up to 24 cycles or until documented PD, withdrawal of consent/assent, treatment becomes intolerable or death, whichever occurs first.

Radiographic response (brain and spine) will be assessed by MRI with and without contrast (ie, gadolinium). Brain MRI assessments will be conducted during screening (within 21 days prior to first dose of study treatment) and then on Day 1 of Cycles 3, 5, 7, 10, 13, 16, 19, 22 (or within 7 days prior to dosing), after completion of Cycle 24 (or within 7 days prior) and as clinically indicated. **Note:** For DIPG subjects only, post-baseline brain MRI assessments will be performed on Day 1 of Cycles 4, 7, 10, 13, 16, 19, 22 (or within 7 days prior to dosing), after completion of Cycle 24 (or within 7 days prior) and as clinically indicated.

Spine MRI will be also performed during screening (within 21 days prior to first dose of study treatment) for all subjects. If no spinal or leptomeningeal disease is present at screening, subsequent spine MRIs will be obtained on Day 1 of Cycles 7, 13, 19 (or within 7 days prior to dosing) after completion of Cycle 24 (or within 7 days prior) and as clinically indicated. If there is spinal or leptomeningeal disease present at screening/baseline, spine MRIs will be obtained at the same time points as the brain MRI as specified above.

A response assessment should also be performed at EOT visit if the subject has discontinued for reasons other than progression of disease and it has been more than 8 weeks since their most recent scan/response assessment.

[figure not shown]
Response evaluations will be performed locally and by independent central reviewer according to criteria detailed in Section 6.4.1.

Subjects who discontinue treatment will enter a Follow-up Period which will continue every 3 months (\pm 14 days) for up to 5 years from enrollment of the last subject, unless consent/assent is withdrawn, the subject is lost to follow-up or dies. Subjects will be followed by phone or clinic visits for emergence of second primary malignancies (SPMs) (regardless of causal relationship), drug-related SAEs, survival status, and start of any new anticancer therapies. Additionally, subjects who discontinue treatment prior to progression will be followed with MRI tumor response disease assessments every 6 months from treatment discontinuation for the first year off treatment, then annually thereafter, until disease progression or until another anticancer therapy is started, whichever comes first.

An external data monitoring committee (DMC) (Section 9.9.2) with multidisciplinary representation will evaluate activity of the study treatment and safety data periodically to monitor benefit-to-risk of this protocol. The function of the DMC is to monitor the safety and activity of the study treatment and to provide recommendations about the study continuation, as appropriate. Details of the DMC structure, composition, and roles/responsibilities will be outlined within a DMC charter.

[figure not shown]
The study will be conducted in compliance with the International Council on Harmonisation (ICH) of Technical Requirements for Registration of Pharmaceuticals for Human Use/Good Clinical Practice (GCP) and applicable regulatory requirements.

Figure 1: Simon’s Optimal Two-Stage Parallel Design

DIPG: Diffused Intrinsic Pontine Glioma
PD: Progressive Disease
OR: Objective Response (CR or PR within 6 cycles)
LTSD: Long Term Stable Disease (SD sustained for ≥ 6 cycles [> 3 cycles for DIPG])

Figure 2: Overall Study Design

ICF = Informed Consent Form; IAF = Informed Assent Form; MRI = Magnetic Resonance Imaging; OS = Overall Survival; PD = Progressive Disease; PFS = Progression Free Survival; SAE = Serious Adverse Event; SPM = Second Primary Malignancy

**From last subject enrolled*

***Subjects without PD at time of treatment discontinuation will continue to be followed for MRI tumor assessments (every 6 months for first year from treatment discontinuation, then annually thereafter)*

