^c Safety laboratory (hematology and serum blood chemistry) and physical examinations do not need to be repeated on Cycle 1, Day 1 if performed within 7 days of starting treatment, unless clinically indicated. FCBP/FCCBP must have pregnancy test performed within 24 hours prior to the initial dosing of pomalidomide.

^d Can also be conducted verbally via phone from the site. Subjects must also be counseled against sharing pomalidomide and donating blood, semen or sperm during therapy until the 28-day post-treatment Safety Follow-up Visit. Pregnancy counseling and potential risks must be conducted on Day 1 of each cycle prior to pomalidomide dispensing or at a minimum of every 28 days during the Treatment Period.

^e Subjects who experience toxicity should have appropriate laboratory testing at least twice weekly (3 to 4 days apart or more frequently) until the toxicity has resolved. It is the responsibility of the Investigator to obtain and review laboratory results for subject safety, and follow up with subjects in a timely manner.

^f Testing with a sensitivity of at least 25 mIU/mL will be performed in FCBP/FCCBP subjects; refer to Section 6.4.2.9 for details. It is the responsibility of the Investigator to obtain and review pregnancy test results for subject safety, and follow up with subjects in a timely manner. The subject may not receive pomalidomide until the Investigator has verified that the result of the pregnancy test performed on Day 1 (within 24 hours prior to treatment) of every cycle is negative.

^g Obtain 10 to 14 days prior to first dose of study drug and again within 24 hours prior to first dose of study drug. **NOTE:** The pregnancy test 10 to 14 days prior to initiation of pomalidomide may be omitted, at the discretion of the investigator, for any FCCBP/FCBP who has high acuity disease requiring immediate treatment with pomalidomide. The pregnancy test within 24 hours prior to the first dose of pomalidomide is required to be performed.

^h Screening/baseline MRI can be obtained up to 21 days prior to Cycle 1 Day 1.

ⁱ Brain/Spine MRIs can be performed within 7 days prior to scheduled timepoint.

^j Response/MRI assessment will be performed at the End of Treatment Visit only if the subject has discontinued for reasons other than PD and has been more than 8 weeks since their most recent scan/response assessment.

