6.2. Treatment Period

The subject will begin treatment upon re-confirmation of eligibility (ie, safety assessments) and subsequent enrollment. The subject must start treatment within 28 days of signing the ICF/IAF. For all subsequent visits, an administrative window of ± 3 days is permitted unless noted otherwise for a particular assessment. Brain and spine MRI assessments can be conducted within 7 days prior to the scheduled timepoint (ie, during study drug rest period). Study visit windows should take into account the subject's investigational product (IP) supply and administration.

Note: Safety laboratory (hematology, serum blood chemistry) and physical examinations do not need to be repeated on Cycle 1, Day 1 if performed within 7 days of starting treatment unless clinically indicated; however, for FCCBP/FCBP subjects, a urine or serum pregnancy test must be performed to assess subject eligibility 10 to 14 days prior to and again within 24 hours prior to the first administration of pomalidomide. The pregnancy test 10 to 14 days prior to initiation of pomalidomide however may be omitted, at the discretion of the investigator, for any FCCBP/FCBP who has high acuity disease requiring immediate treatment with pomalidomide. The pregnancy test within 24 hours prior to the first dose of pomalidomide is required to be performed (refer to Section 6.4.2.9).

The Treatment Period is defined as the time starting from first study drug administration (Cycle 1, Day 1) until permanent study treatment discontinuation. Subjects will be administered pomalidomide on Days 1 to 21 of each 28-day treatment cycle for a maximum of 24 cycles. Pomalidomide will not be administered on Days 22 through 28 of the 28-day treatment cycle.

The following evaluations will be performed at the frequency specified in the Table of Events (Table 4) and further detailed in the protocol referenced Section 6.4. The evaluations should be performed prior to dosing on the visit day, unless otherwise specified.

- Reconfirm eligibility (Cycle 1, Day 1 only)

- IRT registration (Day 1 of each treatment cycle)
- Enrollment via IRT: Day 1, Cycle 1 only
- Concomitant medications and procedures
- Adverse event evaluation
- Assessment of SPM
- Physical examination (including vital signs)
- Height
- Body weight
- BSA calculation
- Lansky/Karnofsky performance status. Karnofsky will be utilized for subjects age ≥ 16 years and Lansky will be utilized for subjects age < 16 years.
- Hematology

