6.3.3. Long-term Follow-up

After permanent study drug discontinuation, all subjects will be followed every 3 months (± 14 days) from the 28-day post-treatment Safety Follow-up Visit for SPMs (regardless of causal relationship), any drug-related SAEs, OS, and start of any new anticancer therapies. Follow-up will continue every 3 months for up to 5 years after the last subject enrollment, unless consent/assent is withdrawn, the subject is lost to follow-up, or death.

Note: The Long-term Follow-up Period may not be terminated because of starting a new anticancer treatment.

In addition, subjects that discontinue treatment prior to disease progression will be followed for MRI tumor response assessments every 6 months from treatment discontinuation for the first year off treatment, then annually thereafter until PD, withdrawal of consent/assent, start of new anticancer therapy, lost to follow up or death, whichever occurs first. These MRI scans will continue to be sent for independent central review.

Survival/long-term follow-up may be conducted by clinic visits, by record review (including public records) and/or telephone contact with the subject, family, or the subject's treating physician.

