6.4. Assessment Types

6.4.1. Efficacy Assessments

Brain tumor assessments will be conducted by MRI with and without contrast (ie, gadolinium) using 3 standard MRI sequences (T1-weighted pre- and postcontrast, T2-weighted, FLAIR). A

spine MRI with contrast (ie, gadolinium) will also be performed as specified in Table 4. The neuroradiologist may select the appropriate sequence that best highlights the tumor (T1-weighted postcontrast or T2-weighted or FLAIR) and the same sequence should be used for serial measurements (Section 6.4.1.2). Further details regarding MRI acquisition requirements are outlined in the Imaging Manual.

Brain MRI assessments will be conducted during screening (within 21 days prior to first dose of study treatment) and then on Day 1 of Cycles 3, 5, 7, 10, 13, 16, 19, 22 (or within 7 days prior to dosing), after completion of Cycle 24 (or within 7 days prior) and as clinically indicated. **Note:** For DIPG subjects only, post-baseline brain MRI assessments will be performed on Day 1 of Cycles 4, 7, 10, 13, 16, 19, 22 (or within 7 days prior to dosing), after completion of Cycle 24 (or within 7 days prior) and as clinically indicated.

Spine MRI will be also performed during screening (within 21 days prior to first dose of study treatment) for all subjects. If no spinal or leptomeningeal disease is present at screening, subsequent spine MRIs will be obtained on Day 1 of Cycles 7, 13, 19 (or within 7 days prior to dosing), after completion of Cycle 24 (or within 7 days prior) and as clinically indicated. If there is spinal or leptomeningeal disease present at screening/baseline, spine MRIs will be obtained at the same brain MRI time points specified above.

In addition, if clinically indicated and at the discretion of the Investigator, CSF cytology will also be assessed to follow disease. It is recommended to follow at the same interval as required brain MRIs if positive at initiation of treatment. Corticosteroid use and clinical assessments (ie, neurologic status) will also be considered when determining overall response (Section 6.4.1.7).

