6.1. Analysis of Primary Efficacy Endpoint

6.1.1. Objective Response and Long-term Stable Disease Rate

The ORSDR is defined as the percentage of subjects that achieve either a CR, PR or SD maintained for ≥ 6 cycles (≥ 3 cycles for the DIPG tumor type/disease indication) as their best response, divided by the total number of subjects available for the analysis within the given population, eg, subjects contained within the Response Population (primary analysis), the ITT Population, and the Safety Population as outlined within Section 5 of this SAP. The ITT Population will not be used should all enrolled subjects have received at least one dose of study drug. Non-responder subjects are considered subjects with a PD as best response, subjects not having a postbaseline assessment or subjects having not evaluable recorded on their postbaseline assessment(s). The corresponding 2-sided, 95% Clopper-Pearson confidence interval (CI) will also be provided.

Calculation of SD duration starts at the time of first dose of pomalidomide and continues until the date of the first observation of PD is recorded or death due to any cause, regardless of whether the subject achieves a CR and/or PR within that period, or until the date of the last disease assessment if no PD or death is recorded; if the difference is ≥ 6 cycles (≥ 3 cycles for the DIPG tumor type/disease indication), ie, the subject has not had a documented PD before Cycle 7, Day 1 (Cycle 4, Day 1 for the DIPG tumor type/disease indication) and has completed 6 cycles of pomalidomide (3 cycles for the DIPG tumor type/disease indication), then the SD will be considered as being maintained for ≥ 6 cycles (≥ 3 cycles for the DIPG tumor type/disease indication).

For identification of PD for this SD duration calculation, PD is classified as a PD as observed during a response assessment (both during the Treatment Period and the Follow-up Period if applicable); the first time this occurrence is observed is selected as the PD date.

Disease assessments recorded on or after start of a new anticancer therapy will not be considered, nor will disease assessments reported after a PD has been observed.

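### Outside DIPG, the plan does not guarantee an end-of-Cycle-6 scan for a child who completes Cycle 6 without PD and stops, and the SAP and protocol classify that child differently on the primary endpoint

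*Protocol*

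**What the plan says.** **Scans on treatment.** Outside DIPG, Protocol 3.1 and 6.4.1 place brain MRI at screening, "then on Day 1 of Cycles 3, 5, 7, 10, 13, 16, 19, 22 (or within 7 days prior to dosing"), after Cycle 24, and whenever clinically indicated. In DIPG the first post-baseline scan is due on Cycle 4 Day 1. Protocol 6.2 explains the early window: "Brain and spine MRI assessments can be conducted within 7 days prior to the scheduled timepoint (ie, during study drug rest period").

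**Scan at EOT.** Protocol 3.1 and 6.4.1 call for a response assessment when a child has "discontinued for reasons other than progression of disease and it has been more than 8 weeks since their most recent scan/response assessment". Protocol 6.2.1 and Table 4 footnote j make the condition exclusive, so that it applies only to a child who "has discontinued for reasons other than PD and has been more than 8 weeks since their most recent scan/response assessment".

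**Scans after stopping without PD.** Protocol 6.3.3 schedules MRI "every 6 months from treatment discontinuation for the first year off treatment, then annually thereafter until PD". New anticancer therapy, withdrawal, loss to follow-up and death also end these scans.

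**Long-term SD in the SAP.** In SAP 6.1.1, repeated in 6.2.2, the SD clock starts at first dose and "continues until the date of the first observation of PD is recorded or death due to any cause". If neither is recorded, it ends at the last disease assessment. Six completed cycles (three in DIPG) are also needed. Assessments on or after the start of new anticancer therapy are disregarded, and SAP 6 rules out imputing missing efficacy data.

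**Long-term SD in the protocol.** Section 6.4.1.7 and Appendix C work by default: a subject with neither an objective response nor progression by the end of Cycle 6 (Cycle 3 in DIPG) has long-term SD.

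**The concern.** The primary endpoint outside DIPG turns on disease status at the end of Cycle 6, and the scan that shows it is the one labelled Cycle 7 Day 1. No text requires that scan of a child who finishes Cycle 6 but does not go on to Cycle 7. The EOT scan is the only other route, and its threshold equals the nominal scan interval. Whether it is required therefore depends on which day the Cycle 5 scan and the EOT visit happened to fall.

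When the scan is missing, the SAP lets a later event stand in for it. A later PD or death lengthens the SD clock and produces a success. Staying alive without a further usable scan leaves the clock at the Cycle 5 scan and produces a failure. The protocol default treats both children alike. The go/no-go counts in each stratum are small enough for one such child to matter.

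**Working it through.** **The plan's own figure.** Protocol 9.3: 9 + 11 subjects, continue on at least 2/9, positive on at least 5/20, for 10% against 40%. With X ~ Bin(9, p) and Y ~ Bin(11, p), P(positive) = sum over x = 2 to 9 of P(X = x) P(Y ≥ 5 − x). This gives 0.0349 at p = 0.10 and 0.9018 at p = 0.40, so the stated 5% and 90% reproduce. The design itself is not in question.

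**Calendar.** Cycles are 28 days (Protocol 6.2), so Cycle c Day 1 falls on Day 28(c − 1) + 1 if nothing is delayed.
- Cycles 3, 5 and 7 Day 1 are Days 57, 113 and 169. Nominal gaps: 113 − 57 = 56 and 169 − 113 = 56.
- With the 7-day early window, the Cycle 5 scan falls on Days 106–113 and the Cycle 7 scan on Days 162–169. The gap runs from 162 − 113 = 49 to 169 − 106 = 63 days.
- The last Cycle 6 dose is on Day 5 × 28 + 21 = 161, and Cycle 6 ends on Day 168.

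**When the EOT scan is required.** For a Cycle 5 scan on Day s and an EOT visit on Day E, the rule fires if E − s > 56, that is, if s ≤ E − 57.

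| EOT visit | Days since a Day 113 scan | Allowed Cycle 5 scan days (106–113) for which it fires |
|---|---|---|
| Day 161 | 48 | 0 of 8 |
| Day 162 | 49 | 0 of 8 |
| Day 165 | 52 | 3 of 8 |
| Day 168 | 55 | 6 of 8 |
| Day 170 | 57 | 8 of 8 |

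With the Cycle 5 scan on Day 113, no EOT visit on Days 161–168 requires a scan. Rewording to at least 8 weeks barely helps: 1 of 8 on Day 162 and 7 of 8 on Day 168.

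**DIPG for comparison.** Screening MRI is up to 21 days before first dose. The end of Cycle 3 (Day 84) is 83 to 104 days later, so the rule always fires if there was no unscheduled scan in between.

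**How one child is classified.** Take SD on Day 113, all Cycle 6 doses taken, and an EOT visit on Day 165. The gap is 52 days, so no scan is required. The next required scan is six months later (taken as 183 days): 165 + 183 = Day 348. Six cycles require 6 × 28 = 168 days.

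| What happens next | SD clock (days) | SAP 6.1.1 and 6.2.2 | Protocol 6.4.1.7 and Appendix C |
|---|---|---|---|
| PD first seen on Day 348 | 348 − 1 = 347 | long-term SD | long-term SD |
| Death on Day 230, no further scan | 230 − 1 = 229 | long-term SD | long-term SD |
| Alive, new therapy from Day 180, no scan before it | 113 − 1 = 112 | failure | long-term SD |

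**Size.** One child is 1/9 = 11 percentage points at Stage 1 and 1/20 = 5 at the end. At the 10% rate, the chance of exactly 1 of 9, one short of Stage 2, is 9 × 0.1 × 0.9^8 = 39%. The documents give no rate for such stops. If a share m of true successes were lost this way (m is assumed), power at 40% × (1 − m) would be 87.3% for m = 5%, 83.8% for 10% and 74.5% for 20%. That shows the loss direction only.

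**The case against.** **The scan is often still obtained.** A reader might infer that every child stopping at the end of Cycle 6 skips the deciding scan. The documents do not support that. The interval is not fixed at 56 days, and with EOT on Day 168 the rule fires for 6 of 8 Cycle 5 scan days. The Cycle 7 scan may already have been done on Days 162–168, and clinically indicated scans are allowed. Toxicity often delays the stop: Table 8 allows up to 14 days for recovery, and a drug held after Day 161 and stopped on Day 175 gives 175 − 113 = 62 days, which fires. All of this stands. It makes the gap rarer, but none of it requires the scan.

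**The error has no established direction.** A reader might infer that the response rate is inflated. A false success needs PD before Day 169 that nobody detected; without that, long-term SD is the right label. The opposite error, a child wrongly counted as a failure, is equally possible. This also stands.

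**The SAP can be read another way.** The clause in SAP 6.1.1 that explains the duration rule, read alone, asks only for no documented PD before Cycle 7 Day 1 and six completed cycles, which would pass the living child too. The failure follows from ending the clock at the last assessment. Two readings of one sentence reinforce the need for clarification.

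**PFS.** A reader might infer that the six-month gap overstates the PFS rates. That is not shown. SAP 4.1 has three-monthly follow-up that covers disease status, SAP 6.2.4 also accepts PD from the disposition forms, and Appendix C lets clinical decline alone count as PD. Likewise, longer unscanned gaps after stopping before the end of Cycle 6 do not bear on long-term SD, because six completed cycles are required.

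**Conclusion.** The point holds in a limited form. In high-grade glioma, medulloblastoma and ependymoma, a child without an earlier CR or PR who completes Cycle 6 without PD and does not start Cycle 7 may have no required scan between Cycle 5 and six months after stopping. For that child, the SAP's date arithmetic rewards a later PD or death and penalises being alive without a qualifying scan, while the protocol default calls every case long-term SD.

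This assumes no cycle delays, an EOT visit in about the last week of Cycle 6, no scan already taken in the Cycle 7 window, and a last cycle with all 21 doses counted as complete. SAP 9.1 uses that last convention for treatment duration; SAP 6.1.1 does not define completion. How often this occurs, and which way it would shift the rates, cannot be found from the documents. It is worth correcting because a single child can decide 2/9 or 5/20 and the remedy is small.

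**What to change.** 1. **Protocol 3.1, 6.2.1, 6.4.1 and Table 4 footnote j.** State that a subject who completes Cycle 6 (Cycle 3 in DIPG) without PD has the already scheduled Cycle 7 Day 1 (Cycle 4 Day 1) scan whether or not the next cycle starts, and before any new anticancer therapy.
2. **SAP 6.1.1 and 6.2.2.** Count long-term SD only with an assessment without PD at the end of Cycle 6 (Cycle 3 in DIPG), with a scan inside the 7-day Cycle 7 Day 1 (Cycle 4 Day 1) window accepted as such. A later PD or death date alone does not qualify. The window needs stating, since a scan on Day 162 gives 162 − 1 = 161 days, short of 168 by strict dates.
3. **Protocol 6.4.1.7 and Appendix C.** Reconcile the default with that rule, so that both documents classify an unscanned child the same way.

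The cost is wording in both documents and one already planned MRI kept for the few children who stop at this point. The downside is that a child who misses that scan counts as a non-success.
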